9.4 Primary Source Documents

The Investigator must maintain primary source documents supporting significant data for each study subject's medical notes. These documents, which are considered "source data", should include documentation of:

- Demographic information
- Evidence supporting the diagnosis/ondition for which the study subject is being studied
- General information supporting the study subject's participation in the study
- General history and physical findings
- Hospitalization or Emergency Room records (if applicable)
- Each study visit by date, including any evaluations, relevant findings/notes by the Investigator(s) occurrence (or lack) of AEs and changes in medication usage, including the date the study drug commenced and completed.
- Any additional visits during the study
- Any relevant telephone conversations with the study subject regarding the study or possible AEs
- An original, signed ICF for study participation
- Subject's diary

The Investigator must also retain all study subject specific printouts/reports of tests/procedures performed as a requirement of the study. During monitoring visits, the monitor will need to validate data in the CRFs against these sources of data.

Confidential Page 73 of 102

9.5 Study Monitoring

will be responsible for monitoring the study according to GCP and applicable regulations. Monitoring visits are for the purpose of confirming adherence to the protocol and to verify complete and accurate data collection. The clinical site will make all records associated with the study available to representative during such visits and audits.

Version No.: 3.0;

The study may be subject to audit by the Sponsor, Sponsor Representative or by regulatory authorities. If such an audit occurs the Investigator must agree to allow access to required subject records. By signing this protocol, the Investigator grants permission to personnel from the Sponsor, its representatives and appropriate regulatory authorities for on-site monitoring of all appropriate study documentation, as well as on-site review of study procedures.

The following should also be available for review:

- 1. Study Subject Screening/Enrollment Log reflecting the reason any study subject screened for the study was found to be ineligible and start and end dates for all study subjects
- 2. Delegation of Authority / Study Personnel Signature Log all site personnel will be listed along with their responsibilities and signatures; to be maintained at the site throughout the study
- 3. Monitoring Log the date and purpose of all monitoring visits by the Sponsor/designee will be documented
- 4. Drug Inventory/Packing Slip reflecting the total amount of drug shipped to the site and received and signed for by the Investigator
- 5. Drug Accountability Log reflecting the total amount of IP dispensed to and returned by each study subject
- 6. Informed Consent Form which must be available for each study subject and be verified for proper documentation
- 7. All correspondence

Monitoring visits will be arranged in advance at a mutually acceptable time with site personnel. Sufficient time must be allowed by the site personnel for the monitoring of CRFs and relevant source documents. The Study Coordinator and/or Investigator should be available to answer questions or resolve data clarifications. Adequate time and space for these visits should be made available by the Investigator.

At the end of the study, a closeout monitoring visit will be performed.

9.6 Audits and Inspections

During the course of the study and/or after it has been completed, one or more site visits may be undertaken by auditors as authorized representatives of the Sponsor. The purpose of the audit is to determine whether or not the study is being conducted and monitored in compliance with the protocol, recognized GCP guidelines and all applicable regulations. Additionally, the study may be inspected by regulatory agencies. These inspections may take place at any time during the study or after the study.

Confidential Page 74 of 102

9.7 Modifications to the Protocol

The procedures defined in the protocol and in the eCRF/paper CRF will be carefully reviewed to ensure that all parties involved with the study fully understand the protocol. In order to ensure the validity of the data, no deviations from the protocol, with minimal exceptions, may be made unless the issue is broad enough to warrant revision of the protocol. Such revisions must be submitted to and have documented approval from the Sponsor and the IRB prior to implementation. All amendments to the protocol, which involve substantial changes in study design, procedure or analyses, will be submitted to appropriate regulatory authority for prior approval.

Version No.: 3.0;

The only circumstance in which an amendment may be initiated without prior IRB approval is to eliminate apparent immediate hazards to a study subject or study subjects. However, the Investigator must notify the Sponsor and the IRB as soon as possible.

9.8 Completion of Study

The Investigator is required to forward CRFs and all other relevant data and records to CRO. The Investigator will complete and report (submission of CRFs) his/her study in satisfactory compliance with the protocol as soon as possible after the completion of the study.

The Investigator must submit a final report to the IRB and CR9 within one (1) month of study completion or discontinuation.

[figure not shown]
A CSR will be prepared in accordance with ICH-GCP and sponsor requirements. In the event the study is prematurely terminated for medical reasons, the principal Investigator or his/her authorized designee will produce an abbreviated safety report.

Confidential Page 75 of 102

10 STUDY SUBJECT INSURANCE

All study subjects will be covered by adequate insurance for any trial related injuries. This insurance covers cost of medical treatment, discomfort or injury to the study subject as a result of drug administration or any of the procedures carried out during the study.

Version No.: 3.0;

Confidential Page 76 of 102

12 PREMATURE TERMINATION OF STUDY/SUBJECT

A subject may terminate from the study early for any reason at any time without any disadvantages. In this case, the Investigator should make every effort to have the subject return to the next scheduled visit to perform all required Study Completion/Early Termination visit activities and to collect and reconcile all test articles. If the subject does not return for the Study Completion/Early Termination visit, the site should fully document the reason for early termination. All data, including the date and primary reason for termination, must be recorded on the Study Completion/Early Termination CRF, and source document.

Version No.: 3.0;

Any subject who experiences an AE may be terminated from the study or from study treatment at any time at the discretion of the Investigator. In this case, the subject should be followed at the discretion of the Investigator until the resolution or stabilization of the AE. All applicable data should be recorded in the AEs section of the CRF. If a subject terminates from the study early for multiple reasons that include AEs, the Study Completion/Early Termination CRF should indicate that early termination was related to an AE.

An exception to this requirement will be the occurrence of an AE that in the opinion of the Investigator is not severe enough to warrant early termination but that requires the use of a prohibited medication, thereby requiring discontinuation of the subject. In such a case, the reason for discontinuation would be the need to take a prohibited medication, not the AE.

The Investigator must inform the clinical project physician/clinical leader/Principal Investigator as soon as possible of all subjects who are being considered for early termination due to AEs. Additional reports must be provided when requested.

The Sponsor reserves the right to terminate the study at any time for administrative reasons. The study may also be terminated by regulatory authorities or by the Investigator for his/her site following consultation with the Sponsor. Following a decision to discontinue the trial, the Investigator will immediately inform both the study subjects and the IRB responsible for this trial within 10 working days, stating the reasons for discontinuation of the study and, furthermore, advise them in writing of any potential risks to the health of study subjects or other persons. It is Sponsor's responsibility to report the premature termination of the study to the regulatory agencies within 15 days providing them with the reasons for the trial discontinuation and advising them in writing of any potential risks to the health of study subjects or other persons. The CRO may notify the regulatory agency on behalf of the Sponsor.

Confidential Page 78 of 102

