4.4 Subject Withdrawal / Dropout

Study subjects will be discontinued from the study for any of the following reasons:

- 1. If the study subject withdraws his or her consent for any reason.
- 2. Subjects who discontinue treatment early due to insufficient or lack of treatment effect or whose condition worsens and require alternate or supplemental therapy for the treatment of moderate to severe persistent facial erythema of rosacea, the subjects should be discontinued, but included in the PP population analysis as treatment failures and provided with effective treatment.
- 3. Subjects that withdraw or discontinue early for reasons other than lack of treatment effect should be excluded from the PP population, but included in the mITT population, using last observation carried forward (LOCF).
- 4. If the study subject's drug code is un-blinded.
- 5. If an AE occurs for which the study subject desires to discontinue treatment or the Investigator determines that it is in the study subject's best interest to be discontinued.
- 6. If the subject experiences an SAE.
- 7. If there is a protocol violation.
- 8. If a concomitant therapy is reported or required which is prohibited or may interfere with the results of the study.
- 9. If the study subject is lost to follow-up.
- 10. If the study subject becomes pregnant (refer to Section 6.5.4)

- 12. Administrative reasons.
- 13. Any other reason that may affect the outcome of the study or the safety of study subjects.
- *A protocol violation is defined as any study subject or Investigator activity that could have possibly interfered with the therapeutic administration of the treatment or the precise evaluation of treatment efficacy that affects the rights, well-being or safety of the subject or the scientific integrity of the study data.

If a subject discontinues participation in the study, every attempt will be made to complete the EoT as indicated in Table 6-1, and any outstanding data and study medication will be collected if possible. The reasons for a discontinuation and the date of removal from the study will be documented on the electronic Case Report Form (eCRF) and Sponsor will be notified.

Before a study subject is considered lost to follow-up, the Investigator will document all attempts to reach the study subject twice by telephone and will send a follow-up letter.

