7.6 Safety Assessment

Safety analyses will be performed on the safety population. No inferential analyses are planned.

The extent of exposure will be summarized using descriptive statistics. Subject exposure to the study medication will be characterized by study duration and treatment duration. Study duration will be defined as number of days from the date of first dosing to the date of EoT visit (Day 29); if the date of EoT visit is missing, the date of the last visit will be used (i.e., date of study visit minus date of first dosing plus 1). Treatment duration will be defined as number of days from the date of first dosing to last dose (i.e., date of last dose minus date of first dose plus 1). Study duration and treatment duration will be summarized using descriptive statistics by treatment group.

Adverse events will be coded using preferred terms and primary SOC from the current version of MedDRA. The AEs and SAEs are considered to be treatment-emergent if they have started or worsened after first application of any study drug up until the EoT visit. The incidence of TEAEs, treatment-emergent SAEs (TESAEs) and drug-related TEAEs and TESAEs will be summarized by treatment group in frequency tables. The maximum severity of a TEAE/TESAE experienced by a subject will be determined by the most severe rating recorded on the eCRF for the subject's given TEAE. TEAEs leading to study discontinuation and treatment-related TEAEs leading to study discontinuation will be summarized by preferred term within primary SOC. Individual subject listings will be generated for TEAEs and TESAEs, including subject age, sex, and race, sorted by primary SOC, preferred term, onset and stop date, onset day relative to the most recent dose, relationship, and severity.

Adverse events will also be collected both for the screening and baseline period (which will be referred to as pretreatment AEs). A listing of pretreatment AEs (including any SAEs) will be presented.

Incidence of concomitant medications will be summarized by treatment group. A listing by subject of all abnormal physical examination values will be provided. The vital signs (body temperature, systolic blood pressure, diastolic blood pressure and heart rate), will be reviewed by the Investigator or qualified delegate and will be summarized by descriptive statistics.

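### An adverse event that forces a prohibited medication is recorded as a non-AE discontinuation, so the disposition table by reason will understate AE-driven withdrawals

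*Protocol*

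**What the plan says.** Protocol section 12 opens with a general rule. If a subject leaves early for several reasons and an AE is among them, the "Study Completion/Early Termination CRF should indicate that early termination was related to an AE". The next paragraph makes an exception for an AE that the investigator considers "not severe enough to warrant early termination but that requires the use of a prohibited medication", where that medication then obliges discontinuation. In that case "the reason for discontinuation would be the need to take a prohibited medication, not the AE".

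Three outputs depend on what is recorded:
- **Disposition.** Protocol 7.5 summarises the primary reasons for discontinuation. SAP 7.2 counts premature discontinuations with their reasons and takes percentages for each reason out of those who discontinued.
- **AE tables, protocol.** Protocol 7.6: "TEAEs leading to study discontinuation and treatment-related TEAEs leading to study discontinuation will be summarized by preferred term within primary SOC".
- **AE tables, SAP.** SAP 7.7.1 lists treatment-emergent AEs (TEAEs) leading to discontinuation of the study medication.

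Protocol 6.5.2.2 gives each AE its own action-taken entry, described as action on study treatment to resolve the event. Protocol 6.5.2.1 also asks that AEs leading to withdrawal of treatment or to significant added therapy be collected and summarised in the study report.

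**The concern.** In the excepted case the sequence is AE, then prohibited drug, then discontinuation. Without the AE the subject would have stayed. Recording only the last link moves an AE-driven exit into another row of the disposition table. Safety and tolerability of Test and Reference is a stated objective (Protocol 2.2, SAP section 2), and discontinuation because of AEs is one of the plainest summaries of tolerability. The exception therefore pushes a safety output in one direction only, downwards. If the same form also feeds the TEAE-discontinuation tables, those fall too, and a reader of the study report could not tell by how much.

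**Working it through.** **Inputs.** Protocol 4.4, 6.5.2.1, 6.5.2.2, 7.5, 7.6 and 12; SAP 6.3, 7.2, 7.6.3.1, 7.7.1 and 8; reaction counts in Table 1 of the prescribing information (Protocol Appendix II, repeated in Protocol Table 1-1). The plan states no figure on this point, so there is none to reproduce. The sample-size text is blank in the public copy.

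**Step 1: disposition table.** In one arm let *A* be the discontinuations triggered by an AE, *m* those of them caught by the exception, and *D* all discontinuations. The AE row shows *A − m* instead of *A*. Under SAP 7.2 its percentage is (*A − m*)/*D* instead of *A*/*D*, a shortfall of *m*/*D*. Because the denominator is *D* and not the number randomised, even a small *m* can be visible. This follows from the text with no further assumption.

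**Step 2: TEAE-discontinuation tables.** The result depends on the source field.
- Built from the termination-form reason: short by *m*.
- Built from the AE form, coded as drug withdrawn: short by 0.
- Built from the AE form, coded as dose not changed: short by *m*. That coding is defensible, because the field asks what was done to resolve the AE, and here the cream is stopped because of the other drug.

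Protocol 7.6 counts events leading to *study* discontinuation, while SAP 7.7.1 counts events leading to discontinuation of the *study medication*. SAP section 8 declares no changes from the protocol, and no visible text names the field. The shortfall therefore lies between 0 and *m* and depends on coding and programming.

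**Step 3: size of *m*.** No discontinuation rates are given. As an assumption, take the two label reactions that look likeliest to need other treatment:
- application site dermatitis: 9/489 = 1.84% active, 0/483 vehicle;
- worsening inflammatory lesions: 7/489 = 1.43% active, 1/483 = 0.21% vehicle;
- sum: 16/489 = 3.27% active, 1/483 = 0.21% vehicle.

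This bounds those two reactions from above. It adds reactions, so one subject may count twice, and it supposes that every event needed a prohibited drug, was judged insufficient to end participation, and ended in discontinuation. It does not cover AEs outside the table. All five listed reactions sum to 30/489 = 6.13%.

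**Step 4: equivalence analysis.** Protocol 4.4 item 3 says that subjects leaving early for "reasons other than lack of treatment effect should be excluded from the PP population". An AE and a need for a prohibited drug are both such reasons, so swapping one label for the other leaves per-protocol (PP) membership unchanged and the shift is zero.

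As a stress test only, suppose a share *f* of Test subjects, all failures, left PP while Reference lost none. The Test rate would go from *p* to *p*/(1 − *f*), a shift of *p·f*/(1 − *f*). With *f* = 16/489 this is *p* × 16/473:
- *p* = 0.15: +0.005
- *p* = 0.30: +0.010
- *p* = 0.50: +0.017

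With *f* = 30/489 it is *p* × 30/459: +0.010, +0.020 and +0.033. Taking the 90% interval as difference ± [1.645 × SE + (1/nT + 1/nR)/2], with an assumed 200 per arm, *p* = 0.30 and *f* = 6.13%, the interval moves from (−0.080, +0.080) to (−0.063, +0.102). With 100 per arm and *p* = 0.50 it moves from (−0.126, +0.126) to (−0.096, +0.161). Both stay inside ±0.20. Such a shift could matter only for a result already close to the limit, and the exception does not produce it.

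**The case against.** The best defence is that section 12 does not contradict itself. It states a rule, labels an exception, and limits it to AEs judged insufficient to end participation. Recording the immediate reason is an accepted convention. The AE is not lost either: section 12 sends the data to the AE section of the case report form, the action-taken and other-treatment entries remain, SAP 7.7.1 lists action taken by subject, and Protocol 6.5.2.1 calls for a summary of AEs that led to withdrawal or significant added therapy.

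Most of this stands. The events stay in the database, and undercounting in the TEAE-discontinuation tables is not established. The defence does not reach the disposition table. The exception tells the site to replace the AE as the reason, and that table is a count of reasons.

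A reader might go further and infer that the exception moves subjects with worsening rosacea out of PP when they should count as failures. The documents do not support that. Protocol 4.4 item 2 is triggered by the clinical circumstance, a subject "whose condition worsens and require alternate or supplemental therapy for the treatment of moderate to severe persistent facial erythema of rosacea", and not by the reason ticked. It says these subjects are "included in the PP population analysis as treatment failures". Item 8 lists prohibited therapy as a ground for discontinuation but contains no PP rule. SAP 6.3 refers PP exclusions to SAP 7.5, which is not in the public text, so nothing can be claimed to be missing there.

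**Conclusion.** The point holds for the disposition table: section 12 requires a label that removes some AE-driven discontinuations from the AE row. For the TEAE-discontinuation tables it is a risk arising from an unnamed source field and two different definitions of discontinuation. The number of subjects is unknown. The 3.3% figure is an upper bound on two reactions, under the assumption that these are the ones needing other treatment, and must not be read as an expected withdrawal rate. If those reactions are the source, the undercount would fall mainly on the active arms and hardly on vehicle. The documents give no basis for expecting it to differ between Test and Reference. There is no material consequence for the equivalence conclusion. The case for change rests on accurate attribution of safety outcomes and on tables that two programmers would build alike.

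**What to change.** 1. On the termination form, record both the AE and the need for a prohibited medication whenever the first led to the second, and reword the section 12 exception to match.
2. In SAP 7.2 and 7.7.1, count any discontinuation triggered by an AE, including through a prohibited medication, as an AE discontinuation. The medication need can be shown as a sub-row.
3. In SAP 7.7.1, name the source field for the TEAE-discontinuation tables, and align study discontinuation (Protocol 7.6) with discontinuation of study medication (SAP 7.7.1), or report both.
4. Confirm in one line that the reason recorded under section 12 does not override Protocol 4.4 item 2.

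Settle the classification while still blind, before database lock. None of this changes who is discontinued or when. The cost is a small protocol and form edit, one derivation in the SAP, and possibly a slightly higher reported AE-discontinuation rate.

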14 LIST OF APPENDICES

Appendix-I: Declaration of Helsinki

Appendix-II: Reference Safety Information (Prescribing Information: RHOFADETM)

Appendix-III: SAE Form

Appendix-IV: Pregnancy Form

Confidential Page 80 of 102

APPENDIX – 1 DECLARATION OF HELSINKI – ETHICAL PRINCIPLES FOR MEDICAL RESEARCH INVOLVING HUMAN SUBJECTS

Adopted by the 18th WMA General Assembly, Helsinki, Finland, June 1964 and amended by the:

29th WMA General Assembly, Tokyo, Japan, October 1975 35th WMA General Assembly, Venice, Italy, October 1983 41st WMA General Assembly, Hong Kong, September 1989

48th WMA General Assembly, Somerset West, Republic of South Africa, October 1996

52nd WMA General Assembly, Edinburgh, Scotland, October 2000 53rd WMA General Assembly, Washington DC, USA, October 2002 (Note of Clarification added)

55th WMA General Assembly, Tokyo, Japan, October 2004 (Note of Clarification added)

59th WMA General Assembly, Seoul, Republic of Korea, October 2008 64th WMA General Assembly, Fortaleza, Brazil, October 2013

Preamble

1. The World Medical Association (WMA) has developed the Declaration of Helsinki as a statement of ethical principles for medical research involving human subjects, including research on identifiable human material and data.

The Declaration is intended to be read as a whole and each of its constituent paragraphs should be applied with consideration of all other relevant paragraphs.

2. Consistent with the mandate of the WMA, the Declaration is addressed primarily to physicians. The WMA encourages others who are involved in medical research involving human subjects to adopt these principles.

General Principles

- 3. The Declaration of Geneva of the WMA binds the physician with the words, "The health of my patient will be my first consideration," and the International Code of Medical Ethics declares that, "A physician shall act in the patient's best interest when providing medical care."
- 4. It is the duty of the physician to promote and safeguard the health, well-being and rights of patients, including those who are involved in medical research. The physician's knowledge and conscience are dedicated to the fulfilment of this duty.
- 5. Medical progress is based on research that ultimately must include studies involving human subjects.
- 6. The primary purpose of medical research involving human subjects is to understand the causes, development and effects of diseases and improve preventive, diagnostic and therapeutic interventions (methods, procedures and treatments). Even the best proven interventions must be evaluated continually through research for their safety, effectiveness, efficiency, accessibility and quality.
- 7. Medical research is subject to ethical standards that promote and ensure respect for all human subjects and protect their health and rights.

Confidential Page 81 of 102

TEVA Pharmaceuticals USA,Inc. Protocol No.: OXY2018-01

Version No.: 3.0; 29 JAN 2020

8. While the primary purpose of medical research is to generate new knowledge, this goal can never take precedence over the rights and interests of individual research subjects.

- 9. It is the duty of physicians who are involved in medical research to protect the life, health, dignity, integrity, right to self-determination, privacy, and confidentiality of personal information of research subjects. The responsibility for the protection of research subjects must always rest with the physician or other health care professionals and never with the research subjects, even though they have given consent.
- 10. Physicians must consider the ethical, legal and regulatory norms and standards for research involving human subjects in their own countries as well as applicable international norms and standards. No national or international ethical, legal or regulatory requirement should reduce or eliminate any of the protections for research subjects set forth in this Declaration.
- 11. Medical research should be conducted in a manner that minimises possible harm to the environment.
- 12. Medical research involving human subjects must be conducted only by individuals with the appropriate ethics and scientific education, training and qualifications. Research on patients or healthy volunteers requires the supervision of a competent and appropriately qualified physician or other health care professional.
- 13. Groups that are underrepresented in medical research should be provided appropriate access to participation in research.
- 14. Physicians who combine medical research with medical care should involve their patients in research only to the extent that this is justified by its potential preventive, diagnostic or therapeutic value and if the physician has good reason to believe that participation in the research study will not adversely affect the health of the patients who serve as research subjects.
- 15. Appropriate compensation and treatment for subjects who are harmed as a result of participating in research must be ensured.

Risks, Burdens and Benefits

16. In medical practice and in medical research, most interventions involve risks and burdens.

Medical research involving human subjects may only be conducted if the importance of the objective outweighs the risks and burdens to the research subjects.

17. All medical research involving human subjects must be preceded by careful assessment of predictable risks and burdens to the individuals and groups involved in the research in comparison with foreseeable benefits to them and to other individuals or groups affected by the condition under investigation.

Measures to minimise the risks must be implemented. The risks must be continuously monitored, assessed and documented by the researcher.

18. Physicians may not be involved in a research study involving human subjects unless they are confident that the risks have been adequately assessed and can be satisfactorily managed.

When the risks are found to outweigh the potential benefits or when there is conclusive proof of definitive outcomes, physicians must assess whether to continue, modify or immediately stop the study.

Vulnerable Groups and Individuals

19. Some groups and individuals are particularly vulnerable and may have an increased likelihood of being wronged or of incurring additional harm.

Confidential Page 82 of 102

TEVA Pharmaceuticals USA,Inc. Protocol No.: OXY2018-01

col No.: OXY2018-01 Version No.: 3.0; 29 JAN 2020

All vulnerable groups and individuals should receive specifically considered protection.

20. Medical research with a vulnerable group is only justified if the research is responsive to the health needs or priorities of this group and the research cannot be carried out in a non-vulnerable group. In addition, this group should stand to benefit from the knowledge, practices or interventions that result from the research.

Scientific Requirements and Research Protocols

- 21. Medical research involving human subjects must conform to generally accepted scientific principles, be based on a thorough knowledge of the scientific literature, other relevant sources of information, and adequate laboratory and, as appropriate, animal experimentation. The welfare of animals used for research must be respected.
- 22. The design and performance of each research study involving human subjects must be clearly described and justified in a research protocol.

The protocol should contain a statement of the ethical considerations involved and should indicate how the principles in this Declaration have been addressed. The protocol should include information regarding funding, sponsors, institutional affiliations, potential conflicts of interest, incentives for subjects and information regarding provisions for treating and/or compensating subjects who are harmed as a consequence of participation in the research study.

In clinical trials, the protocol must also describe appropriate arrangements for post-trial provisions.

Research Ethics Committees

23. The research protocol must be submitted for consideration, comment, guidance and approval to the concerned research ethics committee before the study begins. This committee must be transparent in its functioning, must be independent of the researcher, the sponsor and any other undue influence and must be duly qualified. It must take into consideration the laws and regulations of the country or countries in which the research is to be performed as well as applicable international norms and standards but these must not be allowed to reduce or eliminate any of the protections for research subjects set forth in this Declaration.

The committee must have the right to monitor ongoing studies. The researcher must provide monitoring information to the committee, especially information about any serious adverse events. No amendment to the protocol may be made without consideration and approval by the committee. After the end of the study, the researchers must submit a final report to the committee containing a summary of the study's findings and conclusions.

Privacy and Confidentiality

24. Every precaution must be taken to protect the privacy of research subjects and the confidentiality of their personal information.

Informed Consent

- 25. Participation by individuals capable of giving informed consent as subjects in medical research must be voluntary. Although it may be appropriate to consult family members or community leaders, no individual capable of giving informed consent may be enrolled in a research study unless he or she freely agrees.
- 26. In medical research involving human subjects capable of giving informed consent, each potential subject must be adequately informed of the aims, methods, sources of funding, any possible conflicts of interest,

Confidential Page 83 of 102

TEVA Pharmaceuticals USA,Inc. Protocol No.: OXY2018-01

Version No.: 3.0; 29 JAN 2020

institutional affiliations of the researcher, the anticipated benefits and potential risks of the study and the discomfort it may entail, post-study provisions and any other relevant aspects of the study. The potential subject must be informed of the right to refuse to participate in the study or to withdraw consent to participate at any time without reprisal. Special attention should be given to the specific information needs of individual potential subjects as well as to the methods used to deliver the information.

After ensuring that the potential subject has understood the information, the physician or another appropriately qualified individual must then seek the potential subject's freely-given informed consent, preferably in writing. If the consent cannot be expressed in writing, the non-written consent must be formally documented and witnessed.

All medical research subjects should be given the option of being informed about the general outcome and results of the study.

- 27. When seeking informed consent for participation in a research study the physician must be particularly cautious if the potential subject is in a dependent relationship with the physician or may consent under duress. In such situations the informed consent must be sought by an appropriately qualified individual who is completely independent of this relationship.
- 28. For a potential research subject who is incapable of giving informed consent, the physician must seek informed consent from the legally authorised representative. These individuals must not be included in a research study that has no likelihood of benefit for them unless it is intended to promote the health of the group represented by the potential subject, the research cannot instead be performed with persons capable of providing informed consent, and the research entails only minimal risk and minimal burden.
- 29. When a potential research subject who is deemed incapable of giving informed consent is able to give assent to decisions about participation in research, the physician must seek that assent in addition to the consent of the legally authorised representative. The potential subject's dissent should be respected.
- 30. Research involving subjects who are physically or mentally incapable of giving consent, for example, unconscious patients, may be done only if the physical or mental condition that prevents giving informed consent is a necessary characteristic of the research group. In such circumstances the physician must seek informed consent from the legally authorised representative. If no such representative is available and if the research cannot be delayed, the study may proceed without informed consent provided that the specific reasons for involving subjects with a condition that renders them unable to give informed consent have been stated in the research protocol and the study has been approved by a research ethics committee. Consent to remain in the research must be obtained as soon as possible from the subject or a legally authorised representative.
- 31. The physician must fully inform the patient which aspects of their care are related to the research. The refusal of a patient to participate in a study or the patient's decision to withdraw from the study must never adversely affect the patient-physician relationship.
- 32. For medical research using identifiable human material or data, such as research on material or data contained in biobanks or similar repositories, physicians must seek informed consent for its collection, storage and/or reuse. There may be exceptional situations where consent would be impossible or impracticable to obtain for such research. In such situations the research may be done only after consideration and approval of a research ethics committee.

Use of Placebo

33. The benefits, risks, burdens and effectiveness of a new intervention must be tested against those of the best proven intervention(s), except in the following circumstances:

Confidential Page 84 of 102

TEVA Pharmaceuticals USA,Inc.

Protocol No: OXY2018-01

Protocol No.: OXY2018-01 Version No.: 3.0; 29 JAN 2020

Where no proven intervention exists, the use of placebo, or no intervention, is acceptable; or

Where for compelling and scientifically sound methodological reasons the use of any intervention less effective than the best proven one, the use of placebo, or no intervention is necessary to determine the efficacy or safety of an intervention

and the patients who receive any intervention less effective than the best proven one, placebo, or no intervention will not be subject to additional risks of serious or irreversible harm as a result of not receiving the best proven intervention.

Extreme care must be taken to avoid abuse of this option.

Post-Trial Provisions

34. In advance of a clinical trial, sponsors, researchers and host country governments should make provisions for post-trial access for all participants who still need an intervention identified as beneficial in the trial. This information must also be disclosed to participants during the informed consent process.

Research Registration and Publication and Dissemination of Results

- 35. Every research study involving human subjects must be registered in a publicly accessible database before recruitment of the first subject.
- 36. Researchers, authors, sponsors, editors and publishers all have ethical obligations with regard to the publication and dissemination of the results of research. Researchers have a duty to make publicly available the results of their research on human subjects and are accountable for the completeness and accuracy of their reports. All parties should adhere to accepted guidelines for ethical reporting. Negative and inconclusive as well as positive results must be published or otherwise made publicly available. Sources of funding, institutional affiliations and conflicts of interest must be declared in the publication. Reports of research not in accordance with the principles of this Declaration should not be accepted for publication.

Unproven Interventions in Clinical Practice

37. In the treatment of an individual patient, where proven interventions do not exist or other known interventions have been ineffective, the physician, after seeking expert advice, with informed consent from the patient or a legally authorised representative, may use an unproven intervention if in the physician's judgement it offers hope of saving life, re-establishing health or alleviating suffering. This intervention should subsequently be made the object of research, designed to evaluate its safety and efficacy. In all cases, new information must be recorded and, where appropriate, made publicly available.

Confidential Page 85 of 102

